
Statistical Analysis (by Specific Aim)
	
SA 1: We will use results from the REACT-PD study to establish a calibration of tele-visit (TV) assessments to predict in-clinic MDS-UPDRS scores (Aim 1b). Lin's concordance correlation coefficient, <math>r_c</math>, will be used to summarize accuracy of the calibrated TV estimates vs. scores collected from in-person SURE-PD3 visits conducted close in time, accepting TV estimates as sufficiently accurate if <math>r_c > 0.8</math>. If we observe insufficient concordance, we will recalibrate using all available data from both REACT-PD and the current study.
 
SA 2: The study sample will be randomly split 2:1 into calibration and validation subsets. The calibration sample will be used to derive smartphone (SP) measures that best match the TV assessed composite scores of motor function (MDS-UPDRS part 3), non-motor function (MoCA total score), subjective function (including clinical global impression [CGI] scores, patient global impression scores, modified Schwab and England ADL scores, and MDS-UPDRS parts 1b and 2 scores), and estimates of MDS-UPDRS part 1-3 total scores (Aim 2a). The accuracy of calibrated SP measures will be tested in the reserved validation sample using Lin's concordance correlation coefficient, <math>r_c</math>. If we observe insufficient concordance, we will recalibrate using all available data from both the calibration and validation samples.
 
TV assessments and calibrated SP measures of disease progression will be compared generally and between specific subsets of participants expected to progress at different rates (Aim 2b). Each measure will be standardized to 30% of the observed mean change over 2 years based on a random-slopes linear mixed model of the full sample such that a one-unit change of all standardized, calibrated measures would reflect an equivalent magnitude of change relative to natural rates of progression. Estimated measure-specific variance components will be used to estimate the standard error for a treatment group comparison from a two-arm trial assuming an assessment schedule appropriate for a given measure, e.g., annual for TV measures and quarterly for SP measures. The ratio of squared standard errors will be used to estimate the relative sample size required using one or another measure for designs with equivalent power. The same approach will be used to identify measures that are sensitive to biological subgroups (e.g., among participants stratified by their rate of MDS-UPDRS progression over the first 2 years of in-clinic follow-up in the parent trials) or treatment-based subgroups (e.g., participants randomized to isradipine or serum urate elevation). TV assessments and SP measures will also be compared with respect to their accuracy in predicting future clinical events and changes in

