
	
PROs, e.g., dropping below 80% on the modified Schwab and England ADL, experiencing a fall and other PROs as captured by FI application including PD-PROP measures.
 
SA 3: We will derive novel measures that best predict disease progression using passively collected SP data. We will split the sample 2:1 into discovery and validation subsets, like active tasks. A range of SP measures will be derived from passive data. For walking data (Aim 3a) these include but are not limited to time and frequency domain statistics, energy and entropy of frequency spectrum from the tri-axial accelerometer, along with absolute displacement measurements. For displacement information (Aim 3b) data will be summarized into variables such as furthest distance traveled, frequency of trips, average daily distance etc. Resulting summary metric will then be matched with the TV assessed composite scores of motor function (MDS-UPDRS part 3), Schwab and England ADL scores, MDS-UPDRS (parts 1b and 2 scores), and estimates of MDS-UPDRS part 1-3 total scores. The accuracy of the associations will then be tested in the validation data subset using Lin's concordance correlation coefficient, <math>r_c</math>.
 
Passive measures will be assessed for progression using the same methods as described in SA 2b.

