**2) Reliability:**

*There was excellent correlation between in-person visits and tele-visits for non-motor outcome measures. Intra-class correlation (ICC) coefficients for the Montreal Cognitive Assessment (MoCA), MDS-UPDRS 1A, MDS-UPDRS 1B, and MDS-UPDRS II were 0.78, 0.83, 0.88, and 0.90 respectively. There was good correlation for the MDS-UPDRS Part III (ICC 0.53).*

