### 13.1 Data Processing and Quality Control (QC) for Smartphone (SP) Based Measures:

Data QC and cleaning: As data from the SP are deposited on a daily basis into Synapse, we will have a clear measure of compliance and engagement. Additionally, data streams can be monitored for quality. Data scientists and statisticians at Sage Bionetworks have developed an extensive pipeline to monitor and QC active task measurements from smartphone applications (e.g., <https://github.com/Sage-Bionetworks/mpowertools>). These tools will be adopted and expanded to monitor and QC passive data streams. During the development stage of the application we will run small scale internal experiments where user use Android and iOS devices concurrently to establish bounds on differences between devices.

Data processing/feature extraction: Quality processed data will be summarized into features using extensions of our feature extraction pipelines for active tasks. These include but are not limited to time and frequency domain statistics, energy and entropy of frequency spectrum from the tri-axial accelerometer, along with absolute displacement measurements. For displacement information (Aim 3b) data will be summarized into variables such as furthest distance traveled, frequency of trips, average daily distance etc. Also, additional specific features will be selected based on previously published

studies using passive data and expert knowledge of behavioral patterns of PD patients. These measures will be summarized to a single measure by training a n-fold cross-validated machine learning model using the discovery data subset. Additionally, features will be evaluated by test-retest reliability across time. Data analysis will be performed as described in SA 3.B and 3.C below.

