## 13.2 Statistical Analysis Plan

**Aim 1:** To evaluate concordance between in-clinic and tele-visit MDS-UPDRS assessments (Aim 1b), we will use results from the REACT-PD study to calibrate tele-visit assessments to in-clinic MDS-UPDRS scores, matching means and standard deviations cross-sectionally. We will use Lin's concordance correlation coefficient,  $r_c$ , to summarize accuracy of the calibrated tele-visit estimates vs. scores collected from in-person SURE-PD3 and SUPER-PD visits conducted close in time, accepting tele-visit estimates as sufficiently accurate if  $r_c > 0.8$ . If we observe insufficient concordance, we will investigate contributions of bias, scale difference, and imprecision and re-calibrate using all available data from both REACT-PD and the current study.

**Aim 2:** We will assess the calibration and correlation between tele-visit (TV) and SP metrics both cross-sectionally and longitudinally (Aim 2a). We will generate SP-derived metrics that best match composite scores of motor function (MDS-UPDRS part 3), non-motor function (MoCA total score), subjective function (including global impression (CGI) scores, Schwab and England ADL scores, MDS-UPDRS parts 1b and 2 scores, and estimates of MDS-UPDRS part 1-3 total scores. We will randomly split our sample 2:1 into calibration and validation subsets. For each measure, we will use the calibration sample to develop a transformation of SP data that best matches the TV measurement machine learning models using a variety of machine learning techniques with a final selection based on overall accuracy by 10-fold cross-validation. We will test the accuracy of calibrated SP measures in the reserved validation sample using Lin's concordance correlation coefficient,  $r_c$ . If we observe insufficient concordance, we will investigate contributions of bias, scale difference, and imprecision and re-calibrate using all available data from both the calibration and validation samples.

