We will compare TV vs. calibrated SP measures of disease progression generally, as predictors of future clinical events and changes in patient reported outcomes, and between specific subsets of participants expected to progress at different rates (Aim 2b) due to biology or treatment. After calibration, we will estimate the standard error for a treatment-group comparison from a two-arm trial using measure-specific variance components from a bivariate random-slopes linear mixed model for each pair of TV and SP measures and assuming an assessment schedule appropriate for each measure, e.g., annual for TV measures and quarterly for SP measures. Preferred measures would have smaller standard errors, and specifically, the ratio of squared standard errors provides an estimate of the relative sample size required. We will use the same approach to identify measures that are significantly more sensitive to biological

subgroups (e.g., among participants stratified by their rate of MDS-UPDRS progression over the first 2 years of in-clinic follow-up in the parent trials) or treatment-based subgroups (e.g., participants randomized to Isradipine or serum urate elevation). To compare TV assessments and SP measures with respect to their accuracy in predicting future clinical events and changes in patient reported outcomes, we will use the same 2:1 training: validation split and train separate models using TV and SP metrics collected over the first year of follow-up to predict clinical events and changes in PROs over the second year of follow-up. Clinical events will include dropping below 80% on the modified Schwab and England ADL and experiencing a fall. PROs of interest will include summary scores from the PDQ-8, EQ-5D, and PDAQ-15 and measures derived from the PD-PROP. Selection of the best training models will be based on 10-fold cross-validated accuracy for binary outcomes and residual sum of squares for continuous measures. Positive and negative predictive values of TV and SP-derived predictions will be estimated from the validation sample for binary outcomes and compared by logistic regression. For continuous outcomes, RSS estimates will be compared between TV and SP-derived predictions. As an exploratory analysis, additional models that combine TV and SP measures will be constructed and tested for accuracy relative to models derived from TV or SP measures alone.

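### Section 13.2 (Aim 2b) leaves out the Synopsis step that standardises each measure to its own 2-year change, so its squared-SE ratio is relative sample size only if calibrated smartphone and tele-visit change are equal

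*Combined protocol and SAP*

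**What the plan says.** The Synopsis (Statistical Analysis, SA 2) fixes the scale on which all measures are compared: "standardized to 30% of the observed mean change over 2 years based on a random-slopes linear mixed model of the full sample". It gives the reason: "such that a one-unit change of all standardized, calibrated measures would reflect an equivalent magnitude of change relative to natural rates of progression". Variance components, the standard error for a two-arm comparison and the ratio of squared standard errors come after that step.

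Section 13.2 describes the same Aim 2b comparison. It goes from calibration straight to standard errors, using variance components from a bivariate random-slopes model with, for example, annual TV and quarterly SP assessments. It then concludes: "Preferred measures would have smaller standard errors, and specifically, the ratio of squared standard errors provides an estimate of the relative sample size required". No standardisation to mean change appears there or elsewhere in Section 13. The per-individual norming of displacement features under Aim 3 is a different step.

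On calibration, Section 13.2 (Aim 2a) says: "we will use the calibration sample to develop a transformation of SP data that best matches the TV measurement". The final model is chosen on cross-validated accuracy.

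The method is reused for Aim 3. The Synopsis says: "Passive measures will be assessed for progression using the same methods as described in SA 2b", and Section 13.2 says the same of the displacement features. Section 13.1 says of the passive features: "These measures will be summarized to a single measure by training a n-fold cross-validated machine learning model using the discovery data subset".

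Section 13 calls itself a summary and gives precedence to a separate SAP, which is not among the documents.

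**The concern.** Required sample size is proportional to (SE / effect)². Comparing squared standard errors alone is therefore a sample-size comparison only if both measures are expected to show the same effect in their own units. The Synopsis secures this by dividing each measure by a fixed fraction of its own natural progression. Section 13.2 does not. A measure whose scores are compressed has a smaller standard error and a proportionally smaller effect, and the Section 13.2 rule would credit the first without charging for the second.

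The ratio is Aim 2b's estimate of which platform permits smaller trials, and the same method carries over to the passive measures in Aim 3. An error in it goes directly into a headline result.

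**Working it through.** **The plan's own figure.** Section 13.4 gives an 80% probability of selecting the better measure at an effect size of 0.065 with about 340 participants. It states no formula. One form that matches is 0.8416 × √(2/340) = 0.0645. At 0.065 the probability is Φ(0.065 × √170) = Φ(0.847) = 0.80. So the figure reproduces, and this point does not show it to be wrong. Section 13.4 does not say whether 0.065 refers to the standardised or the unstandardised scale.

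**Identity.** Let Δ be a measure's 2-year mean change and L = Δ_SP/Δ_TV after calibration. On the Synopsis scale each standard error becomes SE/(0.3Δ). The relative sample size is

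R = [SE_SP/(0.3Δ_SP)]² / [SE_TV/(0.3Δ_TV)]² = (SE_SP²/SE_TV²)/L².

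The 0.3 cancels. The Section 13.2 ratio is therefore L²·R.

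| L (assumed) | Section 13.2 ratio ÷ R | Effect on SP sample size |
|---|---|---|
| 0.8 | 0.64 | understated, factor 1/0.64 = 1.56 |
| 0.9 | 0.81 | understated, factor 1/0.81 = 1.23 |
| 1 | 1.00 | correct |
| 1.25 | 1.56 | overstated, factor 1.56 |

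Example: an SP score that is simply 0.8 times the TV score, on the same schedule, carries the same information (R = 1). Section 13.2 would report a ratio of 0.64, a 36% saving that does not exist. The preferred measure is reversed only if R lies between 1 and 1/L², for example between 1 and 1.56 at L = 0.8.

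**Does calibration make L = 1?** Nothing in Section 13.2 constrains mean change. A worked illustration shows how much depends on the method.

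Inputs from the documents: the REACT-PD intra-class correlations (ICCs) in Section 1.2 (Part II 0.90, Part III 0.53), TV at 0, 1 and 2 years, and SP quarterly.

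Assumed inputs: true intercept SD 10, true slope SD 3 per year, 2-year mean change 4 points, complete data, and equal error in both visit modes. SP-specific intercept, slope and residual SDs are A: 4, 2, 5; B: 3, 2, 3; C: 3, 3, 4. Before calibration SP moves one-for-one with the true score.

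- TV error variance = 100(1 − ICC)/ICC = 11.11 (Part II) and 88.68 (Part III).
- TV slope variance = 9 + error variance/2 = 14.56 and 53.34.
- SP slope variance = 9 + SP slope SD² + residual SD²/3.75 = 19.67, 15.40, 22.27 (A, B, C).
- Covariance of TV and SP pooled over the three visits = 100 + 9 × 5/3 + 2.67 = 117.67.
- SP variance pooled = 165.33, 142.33, 157.67. TV variance pooled = 117.67 + error variance = 128.78 (Part II) and 206.35 (Part III).
- Least squares: L = 117.67/SP variance. SD matching: L = √(TV variance/SP variance).

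| Target | R (A/B/C) | Least squares: L | Section 13.2 ratio | SD matching: L | Section 13.2 ratio |
|---|---|---|---|---|---|
| Part II | 1.35/1.06/1.53 | 0.71/0.83/0.75 | 0.68/0.72/0.85 | 0.88/0.95/0.90 | 1.05/0.96/1.25 |
| Part III | 0.37/0.29/0.42 | 0.71/0.83/0.75 | 0.19/0.20/0.23 | 1.12/1.20/1.14 | 0.46/0.42/0.55 |

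Under least squares, all three Part II settings reverse. Under SD matching only B does, where R is close to 1. For Part III nothing reverses under either method, and under SD matching the error runs against SP.

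**Does the concordance criterion exclude L < 1?** No. The least-squares Part II settings give r_c = 0.79/0.86/0.81, so B and C exceed the 0.80 cut-off in Section 13.4 with L of 0.83 and 0.75.

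**The case against.** The strongest reply is that the Synopsis and Section 13.2 belong to one protocol, that Section 13 is expressly a summary, and that nothing in Section 13.2 forbids standardising. The two model descriptions are also compatible: the full-sample model gives the mean change and the bivariate model gives the variance components. Read together they form a correct method. This limits the severity but does not make the Section 13.2 sentence correct. It presents the unstandardised ratio as relative sample size, and an analyst working from it alone would compute a different quantity.

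A second reply is that the plan has other checks. Aim 2a assesses calibration longitudinally, and insufficient concordance leads to an investigation of bias, scale difference and imprecision, then recalibration. These could reveal L ≠ 1, and in the Part III illustration r_c is well below 0.80 under either method (0.58 to 0.69), so those measures would already be flagged. But nothing feeds the result into the ratio, and recalibration is not required to equalise mean change.

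A reader might infer that Section 13.2 systematically favours the smartphone, or would usually pick the wrong platform. The documents do not support that. It follows if calibration is least squares, which is one reading of a best match. Matching means and SDs is another, and it is the rule Section 13.2 spells out for Aim 1. Under it L is nearer 1 and exceeds 1 when TV reliability is low. The variance components behind any reversal are assumed.

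**Conclusion.** The omission and the identity are firm: Section 13.2 and the Synopsis conflict, and the Section 13.2 ratio is L² times the relative sample size. This takes the Synopsis's own definition of equivalent change, an equal fraction of each measure's natural progression. The size is conditional because L is not in the documents: a factor of 1.23 at L = 0.9 and 1.56 at L = 0.8 or L = 1.25, in opposite directions for L below and above 1. If calibration happened to give L = 1, the two descriptions would agree. Reversal of the preferred measure is possible and has not been shown to be likely.

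It also cannot be inferred that the final analysis will be unstandardised, since the SAP takes precedence and is not available. The point should be fixed because the ratio is a main Aim 2b result and the remedy is already in the protocol.

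**What to change.** In Section 13.2, Aim 2b, directly after the reference to calibration, insert the Synopsis step. Each TV and calibrated SP measure is standardised to 30% of its own 2-year mean change, as estimated by the full-sample random-slopes model. Standard errors and their squared ratio are then formed on the standardised measures, with variance components from the bivariate model for each pair. State that this also applies wherever Aim 3 uses the Aim 2b methods, and put the same wording in the SAP.

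The cost is one or two sentences and no change to data collection. There is one statistical cost. Section 13.3 warns that motor progression may be modest in this period, and dividing by a small estimated change makes the ratio noisy. In a simulation under the Part II assumptions above (340 participants, 4-point change), the 95% range of the standardised ratio was 0.86 to 2.24, 0.70 to 1.59 and 0.95 to 2.59 in settings A, B and C. The ratio should therefore be reported with an interval that re-estimates the mean change. It would also help to state in Section 13.4 the scale to which the 0.065 effect size refers.

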#### 13.4 Sample Size Determination

SA 1b. With a sample size of ~10 SURE-PD3 and ~50 SUPER-PD participants expected to complete at least one TV close in time to their in-person clinic visit, the study will have 80% power to conclude that the REACT-PD calibrated tele-visit estimates are sufficiently accurate ( $r_c > 0.8$  at  $\alpha = 0.05$ ) if the true concordance is at least 0.89.

SA 2a. With a 2:1 split of ~340 AT-HOME PD participants, yielding ~115 participants contributing to validation tests, the study will have 80% power to declare a given SP measure sufficiently accurate ( $r_c > 0.80$  at  $\alpha = 0.05$ ) if the true concordance is at least 0.87.

SA 2b. With approximately 80% of participants participating in the SP portion of the study, yielding ~340 participants contributing to the smartphone vs tele-visit comparison, the study would have an 80% probability of selecting the true preferred measure from a pair of TV or SP if the preferred measure had lower standard error by an effect size of at least 0.065.

SA 3. With a 2:1 split of ~240 participants, yielding ~80 in the validation sample and at least 25% experiencing at least an 8-point progression in MDS-UPDS parts 1-3 total score, the study would have 80% power to

declare a novel measure derived from passive SP monitoring to have a ROC AUC significantly greater than 0.80 if the true AUC were at least 0.95.

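### If the binary events are uncommon, cross-validated accuracy separates candidate models poorly in Aim 2b, and an unstated (implicitly 0.5) cut can leave too few people flagged to estimate PPV

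*Combined protocol and SAP*

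**What the plan says.** Section 13.2, Aim 2 (Aim 2b), trains separate TV and SP models on "metrics collected over the first year of follow-up to predict clinical events and changes in PROs over the second year of follow-up". For the sample it states that "we will use the same 2:1 training: validation split", and Section 13.4 (SA 2a) sizes that split: "With a 2:1 split of ~340 AT-HOME PD participants, yielding ~115 participants contributing to validation tests". Two binary outcomes are named: "Clinical events will include dropping below 80% on the modified Schwab and England ADL and experiencing a fall".

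The selection rule is that the best models are chosen "based on 10-fold cross-validated accuracy for binary outcomes and residual sum of squares for continuous measures". The evaluation rule is: "Positive and negative predictive values of TV and SP-derived predictions will be estimated from the validation sample for binary outcomes and compared by logistic regression".

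The documents do not define accuracy for a binary outcome. They give no probability cut, no class weighting, no event rate for either outcome, and no rule for a model that flags nobody. ROC AUC appears only in the SA 3 sample-size statement (synopsis and Section 13.4).

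**The concern.** For a binary outcome, accuracy ordinarily means the proportion correctly classified, by default at a predicted risk of 0.5. Predicting no event for everyone then scores 1 minus the event rate. When events are uncommon, few predicted risks exceed 0.5, so even an informative model scores close to that benchmark and two candidates of different quality can look alike.

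The PPV denominator is the number flagged. If few risks exceed 0.5, that number is small whichever model was chosen.

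The TV-versus-SP comparison of event prediction is part of objective 2b(i). It needs each platform represented by a well-chosen model, and it needs enough flagged people to compare PPV at all.

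**Working it through.** **Inputs from the documents.** About 340 smartphone participants and a 2:1 split (Section 13.4): 340/3 = 113 for validation, in line with the stated ~115, and 340 − 113 = 227 for training. The stated 80% power for SA 2a also reproduces at n = 115: Φ[(atanh 0.87 − atanh 0.80)·√112 − 1.645] = Φ(0.84) = 0.80, with alpha taken as one-sided, which the text does not say. The event-prediction analysis has no sample-size or precision figure of its own.

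**Assumptions.** Event rates p of 10%, 20% and 30%. Binormal risk scores: N(0,1) without the event and N(d,1) with it, where d = √2·Φ⁻¹(AUC). Predicted risks are taken as well calibrated.

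**Formulas.** Flagging everyone whose predicted risk exceeds c means flagging scores above t = d/2 + [logit(c) − logit(p)]/d. Then sensitivity = 1 − Φ(t − d) and false-positive rate (FPR) = 1 − Φ(t). The fraction flagged is q = p·sens + (1 − p)·FPR. The accuracy gain over predicting no events is p·sens − (1 − p)·FPR. PPV = p·sens/q.

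**Number flagged, AUC 0.75 (d = 0.954), c = 0.5.**

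| p | t | sens | FPR | flagged of 113 | accuracy gain |
|---|---|---|---|---|---|
| 10% | 2.780 | 0.034 | 0.0027 | 0.7 | 0.09 points |
| 20% | 1.930 | 0.164 | 0.0268 | 6.1 | 1.15 points |
| 30% | 1.365 | 0.340 | 0.0861 | 18.4 | 4.2 points |

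At 10%, q = 0.0058. The chance that nobody is flagged is (1 − 0.0058)^113 = 0.52. The paired standard error of the 0.09-point gain in 227 people is about √(0.0058/227) = 0.5 points, over five times the gain. With few flagged, PPV says little: the exact 95% interval is 0.01–0.99 for 1 true positive among 2 flagged, and 0.05–0.85 for 2 among 5. The ~15% dropout anticipated in Section 5.1 would reduce 113 to about 96.

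**Choosing between models.** Simulated samples of 227, with candidates of true AUC 0.80 and 0.65. The table shows how often each criterion prefers the better one. Repeat runs differ by about a point.

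| p | accuracy at 0.5 | Brier score or AUC |
|---|---|---|
| 10% | 57% (20% ties) | 95–97% |
| 20% | 89% | 99% |
| 30% | 97% | over 99% |

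**Separating the two causes.** At 10% events and a 0.5 cut, the AUC 0.80 model flags 1.94 of 113 and the AUC 0.65 model essentially none. With ties going to the better model, accuracy selects it 57% + 20% = 77% of the time, so the expected number flagged is 0.77 × 1.94 = 1.5. Selection by Brier score gives 0.95 × 1.94 = 1.8. Changing the criterion alone hardly changes whether PPV can be estimated.

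**Effect of a threshold at the event rate (c = p), AUC 0.75.** Here t = d/2 = 0.477, sens = 0.683 and FPR = 0.317. The numbers flagged are 40, 44 and 48 of 113 at p = 10%, 20% and 30%. PPV is 0.19, 0.35 and 0.48, against 0.58, 0.61 and 0.63 at the 0.5 cut.

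**The case against.** The strongest reply is that the 0.5 cut is not in the plan. The preceding text on Aim 2a uses accuracy loosely, including for models of continuous scores, where percent correct has no meaning. Section 13 says further detail goes into a separate SAP that takes precedence. That SAP is not among the documents, so nothing can be said about whether it covers the point. What remains is that Section 13.2 already names the criterion and sets it against residual sum of squares for continuous measures, which favours the classification reading.

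Several stronger inferences are tempting and are not supported:

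- **That the events are rare.** Section 13.3 expects modest motor progression. Section 1.1, however, has most participants nearing 6–7 years from onset, when disability events begin to appear, and Section 6.1 records falls over 12 months. The 25% in Section 13.4 concerns a different outcome. The rates are simply unknown.
- **That selection becomes a coin toss, or that accuracy rewards flagging nobody.** At 10% events, 57% right and 20% tied leaves 23% wrong, about 2.5 to 1 for the better model. In expectation, a calibrated 0.5 cut never does worse than predicting no events.
- **That selecting by accuracy is what makes PPV inestimable.** The cut does that.
- **That the comparison favours TV or SP.** Both platforms face the same rule.

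The scope is also limited: two named binary outcomes in one component of Aim 2b. The continuous PROs use residual sum of squares, and Aim 2b is sized on standard errors.

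**Conclusion.** The point holds conditionally. If accuracy means percent correct at 0.5 and events run near 10%, the criterion often fails to separate a good model from a weak one (57% against 95–97%), and PPV would rest on about one person flagged or none. At 20% the selection loss is about 10 percentage points and about 6 people are flagged at AUC 0.75. At 30% or more the selection loss is negligible and roughly 18 are flagged. These figures depend on assumed event rates, assumed AUCs and calibrated binormal scores. Because the rates are unknown when the plan is written, a criterion that works across the range is preferable to one that works only at the upper end.

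**What to change.** In Section 13.2 or the separate SAP, select binary-event models on 10-fold cross-validated Brier score (or AUC). Separately, state how the PPV/NPV classification threshold is set: fix it in the training sample, for example at the training event rate, and carry it unchanged to the validation sample for both TV and SP. Both changes are needed, since the first addresses model choice and the second addresses the number flagged.

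The cost is wording only. A threshold rule has to be stated, and PPV will be lower than at a 0.5 cut (0.19 rather than 0.58 at 10% events and AUC 0.75), though estimated from about 40 flagged people rather than fewer than one. Little is gained if event rates prove to be near 30% or higher.
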